#### **4.7 Removal of Subjects from Study Treatment and/or Study as a Whole**

Patients can be taken off the study treatment and/or study as a whole at any time at their own request, or they may be withdrawn at the discretion of the investigator for safety, behavioral or administrative reasons. The reason(s) for discontinuation must be clearly documented on the appropriate electronic case report form (eCRF) and may include:

- Patient voluntarily withdraws from treatment (follow-up permitted)
- Patient withdraws consent (no follow-up permitted)
- Patient is unable to comply with protocol requirements
- Patient demonstrates disease progression
- Patient experiences unacceptable toxicity
- Treating physician determines that continuation on the study would not be in the patient's best interest
- Patient becomes pregnant

- Patient develops a second malignancy that requires treatment which would interfere with this study
- Patient becomes lost to follow-up (LTF)

#### 4.8 Patient Replacement

If a patient is withdrawn from the study prior to completing 21 days of therapy, for reasons other than adverse event or progression of disease, an additional patient may be added. If a patient discontinues treatment due to early progression prior to completing 3 cycles of therapy, the patient will be evaluable for toxicity but not for efficacy endpoints; in this case an additional patient may be added. (*Note: any patient receiving 1 dose of pembrolizumab is evaluable for toxicity but not for primary objective of PFS*).

Patients missing 14 or more doses of capecitabine due to toxicity will not be replaced.

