#### **4.2.3 Continuation of Investigational Therapy after Radiographic Progression (Pseudoprogression)**

Treatment may be continued in the setting of pseudoprogression (radiographic increase or new lesions felt to be due to inflammation/immune response) as long as all of the following criteria are met:

- Absence of clinical symptoms or signs indicating clinically significant PD.
- No significant decline in Eastern Cooperative Oncology Group (ECOG) performance status.
- Absence of rapid PD or threat to vital organs/critical anatomical sites (eg, spinal cord compression) requiring urgent alternative medical intervention
- Patients are made aware of the potential benefits and risks of continuing study therapy in the setting of Pseudo-Progression.

These patients will continue to be monitored for safety parameters. Patients continuing therapy in the setting of suspected pseudoprogression should continue with treatment according to protocol as long as the above criteria are met and clearly documented in the patient's medical record.

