## 5.0 STUDY PROCEDURES

	Screening (-28 days)	On Treatment 		Off Treatment	
Time Period	Baseline	Cycle 1+ (+/- 3days)	After Every 3 cycles	End of Treatment	Follow-up 
Assessment or Activity					
Informed Consent	X				
Medical history (H)	X			X	
Concomitant Medications 	X	X		X	X 
Vitals, Physical exam  (PE) 	X	X		X	
ECOG status	X	X		X	
Toxicity assessment 		X		X	X 
Tumor Measurements 	X		X 	X	
Biopsy/archival tissue 	X				
CBC with diff 	X	X		X	
Chemistry panel 	X	X 		X	
PT/PTT/INR 	X				
Thyroid function tests 	X		X 		
Pregnancy test 	X				
Pembrolizumab 		X			
Capecitabine 		X			
Survival status					X

 Every physical exam will be a full physical exam and is standard of care. It will include vital signs (pulse, temperature, and blood pressure) and height (baseline only) and weight.

 CT c/a/p AND bone scan. In place of bone scan, a PET/CT may be used. If CT is contraindicated, MRI may be used. Any additional imaging such as MRI can be completed at the physician's discretion. The same modality should be used throughout the study. The baseline procedure is to be performed within 28 days prior to registration. Subsequently, it will be done prior to the start of the next treatment cycle e.g 4, 7, 10 etc. For patients who are unable to obtain scans at the designated time points, a window of 7-10 days is allowed. This exception is not applicable to the screening period. Bone scans are to be repeated at each time point ONLY if the patient has bone metastasis or if it is clinically indicated. If the original bone scan during screening is negative, then bone scans are not required in subsequent visits.

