## 6.0 ENDPOINT ASSESSMENT

### 6.1 Disease Definitions

Patients with non-measurable and measurable disease are eligible for this study. Response to treatment will be assessed using RECIST1.1 guidelines (Appendix 3). Response and progression will be assessed in this study via physical exam and imaging. Lesions are defined as either measurable or non-measurable using the criteria provided below.

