### **6.3 Endpoints**

#### **6.3.1 Primary Endpoint(s):**

To evaluate the median progression-free survival (median PFS) for participants receiving pembrolizumab with capecitabine for the treatment of locally advanced or metastatic TNBC and hormone-refractory MBC. This will be assessed by using RECIST 1.1 criteria.

**Complete Response (CR):** Disappearance of all target lesions. Any pathological lymph nodes (whether target or non-target) must have reduction in short axis to <10 mm.

**Partial Response (PR):** At least a 30% decrease in the sum of diameters of target lesions, taking as reference the baseline sum diameters.

**Progressive Disease (PD):** At least a 20% increase in the sum of diameters of target lesions, taking as reference the smallest sum on study (this includes the baseline sum if that is the smallest on study). In addition to the relative increase of 20%, the sum must also demonstrate an absolute increase of at least 5 mm. (Note: the appearance of one or more new lesions is also considered progression).

**Stable Disease (SD):** Neither sufficient shrinkage to qualify for PR nor sufficient increase to qualify for PD, taking as reference the smallest sum diameters while on study.

Please note patients with PD may stay on study with PD if they meet the criteria in section 4.2.3.

*Any patient who has completed **at least 3 cycles** of pembrolizumab and capecitabine will be evaluable for this endpoint.*

*Note: the first set of scans is required to establish that the patient is evaluable for this endpoint.*

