### 6.3.2 Secondary Endpoints:

To describe the objective response rate (ORR) for participants receiving pembrolizumab with capecitabine for the treatment of locally advanced or metastatic TNBC and hormone-refractory MBC.

This will be assessed by using RECIST 1.1 criteria (appendix 3).

*Any patient who has completed **at least 3 cycles** of this combination therapy are evaluable for this endpoint. Note: the first set of scans is required to establish that the patient is evaluable for this endpoint.*

To describe the safety and tolerability of the combination of pembrolizumab and capecitabine for the treatment of locally advanced or metastatic TNBC and hormone-refractory MBC. All adverse events will be assessed by NCT CTCAE 4.03 criteria.

*Any patient who has completed **at least one dose** of either pembrolizumab or capecitabine will be evaluable for this endpoint.*

*(NOTE: If a patient discontinues treatment due to early progression prior to completing 3 cycles of therapy, the patient will be evaluable for toxicity but not for efficacy endpoints; in this case an additional patient may be added).*

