**QualTek Molecular Laboratories**  
**MISP Receiving**  
**[name]**  
**[name]**  
**[contact]**  
**Email: [[contact]](mailto:[contact])**

## 10.0 STATISTICAL CONSIDERATIONS

For PFS, assumptions are that the addition of pembrolizumab will increase PFS to 5  
months compared to historical control of 3 months. Assuming exponential survival, with  
27 evaluable patients, there is 80% power to detect this difference using a one-  
tailed z test at  $p < 0.05$ .

Recruitment of 30 participants to accrue 27 evaluable will last approximately 30 months  
(2.5 years) and participants will be followed for a maximum of 2 years from enrollment of  
the last patient. The primary outcomes chosen is PFS based on mechanism of action..

PFS will be analyzed using a Kaplan-Meier curve. A confidence interval for the median  
PFS will be calculated (Brookmeyer, R. and Crowley, J. (1982), "A Confidence Interval for  
the Median Survival Time," *Biometrics*, 38, 29-41.), and if the confidence interval is  
totally above 3 months, then it may be concluded that the PFS exceeds 3 months.

Objective response rate will be summarized using a proportion and an exact 95% binomial confidence interval. Anti-tumor activity will be reported as a percentage change in the sum of the dimensions of all measurable lesions as defined by RECIST 1.1 criteria. The baseline imaging before treatment will be compared to each subsequent imaging assessment. The maximum anti-tumor activity will be reported using the assessment with the smallest sum of dimensions (maximum response).

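### Patients who stop for progression before completing 3 cycles are dropped from PFS and ORR and may be replaced, so the only efficacy set is selected on the primary outcome and favours the regimen

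*Combined protocol and SAP*

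**What the plan says.** - **Section 4.8 (Patient Replacement).** For a patient who stops for early progression before finishing 3 cycles, "the patient will be evaluable for toxicity but not for efficacy endpoints; in this case an additional patient may be added". A note adds that "any patient receiving 1 dose of pembrolizumab is evaluable for toxicity but not for primary objective of PFS".
- **Section 6.3.1 (primary endpoint).** Anyone with at least three completed cycles "of pembrolizumab and capecitabine will be evaluable for this endpoint", and the first set of scans is needed to establish this.
- **Section 6.3.2 (secondary endpoints).** ORR carries the same 3-cycle and first-scan conditions. A note beginning "If a patient discontinues treatment due to early progression prior to completing 3 cycles of therapy" repeats the exclusion and the replacement option.
- **Section 10.0.** The trial is sized on 27 evaluable patients out of 30 recruited, comparing a 5-month median PFS with a historical 3 months. The conclusion rule is that if the confidence interval for median PFS is "totally above 3 months, then it may be concluded that the PFS exceeds 3 months". The confidence level is not given. No all-treated analysis and no sensitivity analysis is named.
- **Timing of assessments.** Footnote 2 of Section 5.0 says of imaging after baseline: "Subsequently, it will be done prior to the start of the next treatment cycle e.g 4, 7, 10 etc". Section 6.1 adds: "Response and progression will be assessed in this study via physical exam and imaging". The Section 5.0 table schedules a physical exam every cycle.
- **Section 4.2.3.** "Treatment may be continued in the setting of pseudoprogression", subject to conditions that include no clinically significant or rapid progression.

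**The concern.** Three cycles last about 9 weeks, which falls inside the 3-month benchmark. Every patient dropped under this rule has an event before 3 months, and that event leaves the data to which the success rule is applied. No matching 9-week condition is stated for the historical 3 months, and with one arm there is no concurrent group in which the distortion could cancel. Median PFS and ORR both move up, and so does the chance of declaring success for a regimen no better than the benchmark. Because no all-treated result is planned, the report need not show the shift.

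Not every early event is lost. Progression first seen on the scan before cycle 4 counts, and a patient continuing under Section 4.2.3 can still complete 3 cycles. The patients at risk of removal are those whose progression is called earlier, by physical exam or additional imaging. Sections 4.8 and 6.3.2 write a rule for exactly that case.

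**Working it through.** **The plan's own figure.** On the log-hazard scale, a one-sample exponential z test (one-sided 0.05, 80% power, medians 5 against 3) needs ((1.645 + 0.842)/ln(5/3))² = 23.7, so 24 events. Assuming a 10% allowance, 24/0.9 gives 27 after rounding up. Enrolment is 27/0.9 = 30. The plan does not state which variant was used; the hazard-scale version gives 28.9. The 27 is therefore reproducible, but the calculation treats PFS times as an unselected exponential sample.

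**Inputs.** The null median is 3 months, exponential (Section 10.0). Three cycles = 9 weeks = 63/30.4375 = 2.07 months (Section 6.3.3 for the 9 weeks). There are 30 enrolled and 27 evaluable (Section 3.0). Not in the documents, so shown as ranges:
- the number of early progressors dropped, or equivalently f, the share of patients with an event before week 9 who are dropped;
- the confidence level (95% and 90% both shown).

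**Early events under the null.** S(t) = 2^(−t/3), so S(2.07) = 0.620 and q = 0.380. Of 30 patients, 11.4 are expected to have an event before week 9.

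**Success threshold.** With no censoring before 3 months, the lower Brookmeyer-Crowley limit exceeds 3 months when KM(3) − 0.5 > z × SE, with SE = √(KM(3)(1 − KM(3))/n). For n = 27, 19 beyond 3 months gives z = 2.32 and 18 gives z = 1.84, so the thresholds are 19 (95%) and 18 (90%).

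**Dropping k of 30.** The dropped patients all had events before 3 months. The number beyond 3 months therefore stays Binomial(30, 0.5), while the threshold falls to that for 30 − k patients. The shifted median is 3 × (1 − log₂(1 − k/30)).

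| Dropped | Analysed | Threshold 95% / 90% | False success 95% / 90% | Median (months) |
|---|---|---|---|---|
| 0 | 30 | 21 / 20 | 2.1% / 4.9% | 3.00 |
| 1 | 29 | 20 / 19 | 4.9% / 10.0% | 3.15 |
| 3 | 27 | 19 / 18 | 10.0% / 18.1% | 3.46 |
| 6 | 24 | 17 / 16 | 29.2% / 42.8% | 3.97 |

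Three dropped is the whole 30 − 27 allowance. It needs 3/11.4, about a quarter, of the expected early events. Simulation of 200,000 trials agrees (3 dropped: 10.0% / 18.1%; 6 dropped: 29.1% / 42.7%).

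**Replacing until 27 are evaluable.** The kept fraction is 1 − qf, and S(3 | kept) = 0.5/(1 − qf). The median is 3 × (1 − log₂(1 − qf)) and the number enrolled is 27/(1 − qf). A true ORR of 20% reads as 0.20/(1 − qf); the 20% is illustrative, taken from the paclitaxel-refractory study in Section 1.2.2.

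| f | Median | False success 95% / 90% | Enrolled | ORR |
|---|---|---|---|---|
| 0 | 3.00 | 2.6% / 6.1% | 27 | 20.0% |
| 0.10 | 3.17 | 4.1% / 9.0% | 28 | 20.8% |
| 0.25 | 3.43 | 8.1% / 15.9% | 30 | 22.1% |
| 0.50 | 3.91 | 23.7% / 37.7% | 33 | 24.7% |
| 1 (upper bound) | 5.07 | 94% / 98% | 44 | 32.3% |

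**The case against.** **The test.** Section 10.0 also names a one-tailed z test, and on that test the inflation is smaller. Simulation on the log-hazard scale gives 3.6%, 5.0%, 8.7% and 18.1% with 0, 1, 3 and 6 dropped. On the hazard scale with null variance it gives 1.6%, 2.3%, 4.2% and 9.2%. This stands as a point about size. However, the z test appears only in the power statement, while the confidence interval is the stated basis for the conclusion. The error rises with the number dropped under either.

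**Event times.** The figures assume progression is dated when it happens, yet scans come only every 9 weeks. If every progression waited for a scan, anyone clear at week 9 would count as beyond 3 months. With nobody dropped, false success would be P[Bin(30, 0.620) ≥ 21] = 24% (95% CI) or P[≥ 20] = 37% (90% CI). That is a fair caveat on the absolute percentages. It is a separate effect, from scan timing, and it depends on how the historical median was measured, which the documents do not say. It does not remove the bias from exclusion.

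**How many can be lost.** Section 6.2 prefers imaging to clinical exam, and Section 6.2.1 accepts only superficial, caliper-measured clinical lesions, so f may be small. With accrual held at 30 and 27 evaluable required, at most three can be lost, from all causes. Both points stand. The rows for 6 dropped, f = 0.50 and f = 1 lie outside the plan and only show the trend. The conclusion rests on one to three dropped.

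**Visibility.** Reasons for discontinuation are recorded (Section 4.7), end-of-treatment tumour measurements are scheduled (Section 5.0), and follow-up for PFS continues (Section 4.6). The data would therefore exist. What is missing is a planned analysis that uses them.

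**Conclusion.** The concern holds, and the plan is wrong as written on this point. The exclusion, the replacement option and the absence of any other efficacy set are all explicit, and the direction of bias is toward success. Within the planned 30 patients, one dropped early progressor roughly doubles the false-success rate. Three take it from 2.1% to 10.0% with a 95% interval, or from 4.9% to 18.1% with a 90% interval, and lift a true 3-month median to 3.46 months. ORR is descriptive and shifts modestly.

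These sizes assume exponential PFS with a true median of 3 months, exact event times, no censoring before 3 months, and use of the confidence-interval rule. The actual number dropped is unknown. If all progression is first seen on the scan before cycle 4, f = 0 and this rule adds no bias. Read literally, the 3-cycle condition also removes early deaths and early toxicity stops, which are not quantified here.

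Section 4.8 also conflicts with itself. Its first sentence does not allow replacement for progression before 21 days, while its second allows it at any time before 3 cycles are complete.

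**What to change.** Amend Sections 4.8, 6.3.1, 6.3.2 and 10.0 as follows:
- Define the primary analysis set for PFS and ORR as all patients who receive at least one dose of study treatment.
- Count progression or death before 3 cycles as a PFS event on its date and as a non-response.
- Keep patients who stop early for other reasons in the set, followed under Section 4.6 and censored in the usual Kaplan-Meier way if no event is seen.
- Do not replace patients for progression. Reword the first two sentences of Section 4.8 so that they agree, and change its note on PFS evaluability to match.
- Retain the 3-cycle evaluable set only as a labelled sensitivity analysis, reporting how many patients it excludes and why.

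The cost is protocol wording: no extra patients and no extra procedures. If any early progressors occur, the reported median PFS and ORR will be less favourable than under the present rule.

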#### 4.9 Supportive Care Guidelines & Toxicity Management

Subjects should receive appropriate supportive care measures as deemed necessary by the treating investigator. Suggested supportive care measures for the management of adverse events with potential immunologic etiology are outlined below. Where appropriate, these guidelines include the use of oral or intravenous treatment with corticosteroids as well as additional anti-inflammatory agents if symptoms do not improve with administration of corticosteroids. Note that several courses of steroid tapering may be necessary as symptoms may worsen when the steroid dose is decreased. For each disorder, attempts should be made to rule out other causes such as metastatic disease or bacterial or viral infection, which might require additional supportive care. Toxicity will be attributed to either or both drugs per physician's clinical judgement, and dose modifications/delays will be made accordingly.

Note: if after the evaluation the event is determined not to be related, the investigator is instructed to follow the treatment guidance (as outlined below)

It may be necessary to perform conditional procedures such as bronchoscopy, endoscopy, or skin photography as part of evaluation of the event. Refer section 4.3 for dose modification.

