**Prohibited Concomitant Medications**

Subjects are prohibited from receiving the following therapies during the Screening and Treatment Phase (including retreatment for post-complete response relapse) of this trial:

- Antineoplastic systemic chemotherapy or biological therapy
- Immunotherapy not specified in this protocol
- Chemotherapy not specified in this protocol
- Investigational agents other than pembrolizumab
- Radiation therapy

*Note: Radiation therapy to symptomatic lesions or to the brain may be allowed at the investigator's discretion.*

- Live vaccines within 30 days prior to the first dose of trial treatment and while participating in the trial. Examples of live vaccines include, but are not limited to, the following: measles, mumps, rubella, varicella/zoster, yellow fever, rabies, BCG, and typhoid vaccine.
- Systemic glucocorticoids for any purpose other than to modulate symptoms from an event of clinical interest of suspected immunologic etiology.

Subjects who, in the assessment by the investigator, require the use of any of the aforementioned treatments for clinical management should be removed from the trial. Subjects may receive other medications that the investigator deems to be medically necessary.

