##### 4.9.2 Diarrhea/Colitis:

Subjects should be carefully monitored for signs and symptoms of enterocolitis (such as diarrhea, abdominal pain, blood or mucus in stool, with or without fever) and of bowel perforation (such as peritoneal signs and ileus).

- All subjects who experience diarrhea/colitis should be advised to drink liberal quantities of clear fluids. If sufficient oral fluid intake is not feasible, fluid and electrolytes should be substituted via IV infusion. For Grade 2 or higher diarrhea, consider GI consultation and endoscopy to confirm or rule out colitis.
- For **Grade 2 diarrhea/colitis** that persists greater than 3 days, administer oral corticosteroids.

- For **Grade 3 or 4 diarrhea/colitis** that persists > 1 week, treat with intravenous steroids followed by high dose oral steroids.
- When symptoms improve to Grade 1 or less, steroid taper should be started and continued over no less than 4 weeks.

**4.9.3 Type 1 diabetes mellitus (if new onset, including diabetic ketoacidosis [DKA]) or  $\geq$  Grade 3 Hyperglycemia, if associated with ketosis (ketonuria) or metabolic acidosis (DKA)**

For **T1DM** or **Grade 3-4** Hyperglycemia

- Insulin replacement therapy is recommended for Type I diabetes mellitus and for Grade 3-4 hyperglycemia associated with metabolic acidosis or ketonuria.
- Evaluate patients with serum glucose and a metabolic panel, urine ketones, glycosylated hemoglobin, and C-peptide.

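### The note in section 4.9 sends events judged not related into guidance written for immune events, out of line with that section's scope and, once a non-immune cause is established, with the steroid restriction in section 4.4 (minor, patient safety)

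*Combined protocol and SAP*

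**What the plan says.** Section 4.9 sets its own scope: "Suggested supportive care measures for the management of adverse events with potential immunologic etiology are outlined below". It then asks for a differential diagnosis: "attempts should be made to rule out other causes such as metastatic disease or bacterial or viral infection, which might require additional supportive care". The paragraph closes on attribution ("Toxicity will be attributed to either or both drugs", by the physician's clinical judgment). A separate note follows: "if after the evaluation the event is determined not to be related, the investigator is instructed to follow the treatment guidance (as outlined below".

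The subsections below the note direct corticosteroids for pneumonitis (4.9.1), diarrhea/colitis (4.9.2), hypophysitis (4.9.4), Grade 3-4 hyperthyroidism (4.9.5), hepatic events (4.9.6) and renal failure or nephritis (4.9.7). For example, 4.9.2 says of Grade 2 diarrhea/colitis "that persists greater than 3 days, administer oral corticosteroids". They also contain measures that are not immunosuppressive, such as fluids, insulin, beta-blockers and thyroid replacement.

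The list of prohibited concomitant medications in section 4.4 includes "Systemic glucocorticoids for any purpose other than to modulate symptoms from an event of clinical interest of suspected immunologic etiology". Subjects who, in the investigator's assessment, "require the use of any of the aforementioned treatments for clinical management should be removed from the trial". The same paragraph ends: "Subjects may receive other medications that the investigator deems to be medically necessary".

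**The concern.** The evaluation in section 4.9 is there to separate events that may be immune-mediated from events with another explanation. One would expect the note to say that events found to have another explanation leave the pathway. It says that they follow it, and it gives no instruction for events that are related.

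What is at stake is how an individual patient is managed. Steroids given for an infection, or for a liver-test rise caused by metastases, would be treatment for a cause that the work-up has already excluded. The site would also be using a drug class that section 4.4 does not allow for that purpose. The situation is foreseeable in this population. Footnote 5 to the section 5.0 schedule provides extra liver tests for patients with liver metastases, and section 8.2.10 lists diarrhea and raised bilirubin among the capecitabine effects seen in more than 10% of patients.

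**Working it through.** No arithmetic applies, because the plan states no figure on this point. The check is a reading of the relevant texts against each other.

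1. **Scope against note.** The scope sentence covers events that may be immunologic. The note covers events determined not to be related. An event traced to infection or metastatic disease, the causes section 4.9 itself names, is outside the first and inside the second. The note therefore runs against the section it belongs to, whatever section 4.4 says.

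2. **What *related* means.** The note does not define it.
   - If it means related to a study drug, which the preceding sentence on attribution suggests, an unrelated event could still have a suspected immune cause. Steroids for it might then fall within the exception in section 4.4.
   - If it means immune-related, capecitabine diarrhea counts as not related and is pointed to the steroid step in 4.9.2, although capecitabine toxicity has its own rules in section 4.3.
   - On either reading, an event shown to be infectious or metastatic is not related.

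3. **Note against section 4.4, for an established non-immune cause.** Take Grade 2 diarrhea lasting more than 3 days and found to be infectious.
   - Section 4.9, note: follow the guidance below. Section 4.9.2 then gives oral corticosteroids.
   - Section 4.4: an immunologic cause is no longer suspected, so systemic glucocorticoids are not permitted, and a subject judged to require them should leave the trial.

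   A Grade 3-4 liver-test rise attributed to metastases gives the same result through 4.9.6, which directs intravenous corticosteroids. In both cases the steroid step cannot be carried out consistently with section 4.4. The non-steroid measures, such as fluids for diarrhea, can.

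4. **Whether other text resolves it.** Table 1 in section 4.3.1 is titled for immune-related events, and 4.9.9 asks for other etiologies of suspected myocarditis to be excluded. Both fit the scope sentence better than the note, but neither overrides the note or forbids treating an unrelated event. In the amendment history, Amendment 2 added the attribution sentence and subsections 4.9.8 and 4.9.9, and Amendment 5 repaired the reference to Table 5 in 4.9.10. No entry rewords the note.

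**The case against.** The strongest reply is that nothing here is a mandate. Section 4.9 calls its measures suggested, gives supportive care as the investigator deems necessary, and uses steroids where appropriate. Section 4.4 leaves the final decision on supportive therapy to the investigator and/or the primary physician. A sensible investigator can follow both sections by using the non-steroid measures and treating steroids as inappropriate for an infection. Section 4.9.2 also advises considering GI consultation and endoscopy to confirm or rule out colitis. The note could even be read as saying that general supportive care continues whatever the attribution.

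Much of this stands. A reader might infer that sections 4.9 and 4.4 impose commands that cannot both be obeyed, or that the protocol compels steroids for an infection. The discretionary wording does not support either inference. A reader might also infer that a negation was dropped from the note. That is plausible from the logic of the section, but the documents do not state the intended wording.

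What does not stand is the suggestion that discretion makes the sentence harmless. The note says the investigator is instructed to follow the guidance, and it does not limit this to general measures. The permission for other medically necessary medications comes after the prohibited list, so it does not lift the steroid restriction.

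**Conclusion.** The note is wrong as written, and the point is minor. It is out of line with the scope of section 4.9 in every case where another cause has been found. It is inconsistent with section 4.4 in a narrower set: events with an established non-immune cause for which a steroid step would be used. That narrower conclusion assumes that immunologic etiology is no longer suspected once work-up has identified infection, metastatic disease or another non-immune cause. It does not extend to every event judged unrelated to study drug.

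The size cannot be put as a number of patients, since the documents give no rate of such events or of steroid use for them. Harm is unlikely because the guidance is advisory and clinicians are asked to look for the cause. A reader might infer some effect on the trial's results through the removal rule in section 4.4. The documents do not support this: removal depends on the investigator judging that a prohibited treatment is required, and the endpoint definitions and the power statement in section 10.0 do not depend on the note.

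**What to change.** Replace the note with a sentence to this effect: *If, after the evaluation, the event is determined not to be immune-related (e.g., infection, metastatic disease or capecitabine toxicity), the investigator does not need to follow the corticosteroid and other immunosuppressive steps below and should treat the identified cause; general supportive measures and Table 5 for infusion reactions still apply, and capecitabine toxicity is managed under section 4.3 (Tables 2-4 and the non-hematologic toxicity paragraph).*

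This replaces the undefined term *related* with the distinction that the section turns on. It keeps the fluid advice for all subjects with diarrhea. It keeps Table 5, because section 8.1.10 says infusion reactions are not considered immune mediated. Naming the non-hematologic toxicity paragraph matters because Tables 2-4 do not cover hepatic or renal events.

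The cost is one sentence in an amendment and a notice to the study team. No visits, procedures or data are added.
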